### **8.3 Formulation of Test and Control Products**

#### **8.3.1 Formulation of Test Product**

The test product will be comprised of 1200mg alpha-lipoic acid formulated for oral administration with no identifiable markings. ALA is currently commercially available from a variety of manufacturers and suppliers. For our mouse experiments, we used alpha lipoic acid sold by GNC. In our lab, purity testing with mass spectrometry revealed that this ALA contained no significant additional materials outside of ALA. Since this is a commercially available product with tablet markings on it, we will obtain our alpha lipoic acid from the Wellspring Pharmacy. (<https://wellspringrx.com/>). Wellspring Pharmacy maintains strict adherence to all regulations set by the California Board of Pharmacy. The requested formulation of ALA for this study will be two tablets containing 600 mg ALA. Wellspring Pharmacy will maintain control of the test product and provide it to the study team in packaging identical to placebo packaging.

#### **8.3.2 Formulation of Control Product**

The control product will be designed to appear identical as the test product to serve as the placebo. It will contain 10 mg sucrose and be obtained from Wellspring Pharmacy (<https://wellspringrx.com/>). Wellspring Pharmacy maintains strict adherence to all regulations set by the California Board of Pharmacy.

### 8.3.3 Packaging and Labeling

Because both participants and study team members will be blinded to treatment arm, the test product and control products will appear identical.

*Packaging:* Study supplement or placebo is supplied in cartons containing 240 tablets (a four-month supply). The tablets will be packaged in sets of 60 enclosed within a plastic bottle. Four bottles will be contained in each carton.

*Labeling:* Each carton of study supplement or placebo will be labeled with the required FDA warning statement, the protocol number, a treatment number, the name of the sponsors, and directions for patient use and storage. Each tablet will be labeled with the study protocol number.

## 8.4 Supply of Study Drug at the Site

The Test Product and Control Product will be stored in a locked cabinet in a locked office at the Compounding and Research Support Pharmacy at UCSF. There will only be one study site. After participants are randomized, treatment packages will be provided to the study coordinator who will provide them to study participants. Pill counts will be performed during each clinical visit and extra study drugs will be discarded. During clinical visits, if more study treatment packages are needed, they will be requested from the Compounding and Research Support Pharmacy at UCSF and provided to participants.

### 8.4.1 Dosage/Dosage Regimen

600 mg of the ALA supplement or placebo will be taken orally twice daily for three years. The pharmacology of ALA is such that bioavailability should be highest three hours after administration. Participants will be encouraged to take the study tablet at night prior to bed to facilitate consistent bioavailability between participants.

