	pregnancy during the study duration; unable to give informed consent; non-English primary language; pregnancy, lactation, or child- bearing age without birth control devices; and serious illness likely to cause death within the next 5 years.
TEST PRODUCT, DOSE, AND ROUTE OF ADMINISTRATION	The test product is 600 mg of ALA administered orally twice a day for three years.
CONTROL PRODUCT, DOSE AND ROUTE OF ADMINISTRATION	The control product is a sucrose tablet containing 10 mg of sucrose, given orally twice a day for three years.
DURATION OF PARTICIPATION AND DURATION OF STUDY	Screening: 1 week to determine eligibility Treatment: 3 years with visits every 4 months Follow-up: 2 years with visits every 4 months

CONCOMITANT MEDICATIONS	
Allowed: The participants will be allowed to continue any medications they are currently taking.
 
Prohibited: No medications will be strictly prohibited. However, alpha-mercaptobutyrylthiolglycine and D-penicillamine, two medications currently used to treat cystinuria, are both thought to bind the sulfhydryl groups of cysteine preventing the molecules from binding together and resulting in the insoluble cystine molecule. Both medications are not used with great frequency and both are not very effective. As they may interfere with the mechanism of action of ALA, participants of this study who take alpha-mercaptobutyrylthiolglycine and/or D-penicillamine will be asked to stop these medications 12 weeks prior to starting the treatment portion of the study as a washout period to ensure no harmful effects result from stopping these therapies. If they chose not to stop, at the discretion of the Principal Investigator, the participant will be allowed to participate and the study will simply document the use of Thiola throughout the course of the study and may look at these participants separately in the final analysis.

EFFICACY EVALUATIONS	Efficacy evaluations will include determination of stone recurrences on clinical history, exam, and radiographic review; quantitative 24-hour urinary cystine; and urinary, blood, and stone metallomic and metabolomic profiling.

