## 8 STUDY TREATMENTS

### 8.1 Method of Assigning Participants to Treatment Groups

Participants will be computer sequence-randomized to receive either oral daily dosing of 1200 mg ALA or placebo.

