### 8.4.2 Dispensing

The ALA supplement or placebo will be given to the participant with sufficient quantity for administration at home, with a 4-month supply (240 tablets) to be given at each interval visit. At subsequent visits, remaining pills will be counted and counts recorded to reflect compliance for participants.

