### 8.4.3 Administration Instructions

The ALA supplement or placebo is to be taken orally twice daily.

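### Section 8.4.1 sets twice-daily dosing and then advises taking a single study tablet at bedtime, and nothing in the protocol reconciles the two

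*Combined protocol and SAP*

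**What the plan says.** The operative dosing text is Section 8.4.1. It opens with "600 mg of the ALA supplement or placebo will be taken orally twice daily for three years", remarks on when bioavailability peaks, and then says: "Participants will be encouraged to take the study tablet at night prior to bed to facilitate consistent bioavailability between participants".

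The regimen also appears in three other places:

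- Synopsis: "The test product is 600 mg of ALA administered orally twice a day for three years".
- Section 8.4.3: "The ALA supplement or placebo is to be taken orally twice daily".
- Section 8.1: participants are "computer sequence-randomized to receive either oral daily dosing of 1200 mg ALA or placebo".

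None of the three gives a time of day, and Section 8.1 gives a daily total without a split.

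On product and supply, Section 8.3.1 describes a 1200 mg test product and then says: "The requested formulation of ALA for this study will be two tablets containing 600 mg ALA". Section 8.3.3 puts 240 tablets in a carton and calls that four months' supply. Section 8.4.2 dispenses product "with a 4-month supply (240 tablets) to be given at each interval visit". Under Section 8.4, after each pill count, "extra study drugs will be discarded", and further packages can be requested during clinic visits. Visits on treatment are every 4 months for 3 years. No overage and no visit window is stated.

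The checks on intake are a coordinator contact at 3-4 weeks (Sections 5.2 and 8.5), a diary (Section 8.6), and pill counts from Visit 2 onward (Sections 10.2 and 10.3). The primary analysis is by intention to treat (Section 15.2).

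**The concern.** A participant cannot act on both statements in Section 8.4.1 without guessing how they fit together. The bedtime sentence is advice meant for participants, and Section 8.3.3 requires directions for use on the carton, so the ambiguity can travel from the protocol to the people taking the product.

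What is at stake is the delivered intervention. A participant in the active arm who takes one tablet a night receives half the intended amount and is still analysed as randomized. That pulls the observed difference toward zero in a trial with 25 participants per arm. The protocol's own reason for the sentence is consistency between participants, and an instruction open to several readings works against that aim.

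**Working it through.** **Step 1. Reproduce the plan's supply figure.** Inputs: 240 tablets per four months (Sections 8.3.3 and 8.4.2) and twice-daily intake (Section 8.4.3). With 30-day months, 2 × 4 × 30 = 240, so the figure reproduces exactly. It implies two tablets a day and, for 1200 mg a day, 1200 / 2 = 600 mg per tablet.

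**Step 2. Set out the readings of the bedtime sentence.** Assume 600 mg per tablet, a 122-day interval and full adherence to the reading in question.

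| Reading | Tablets per day | Daily intake | Share of plan | Tablets left from 240 |
|---|---|---|---|---|
| One tablet nightly | 1 | 600 mg | 600/1200 = 50% | 240 − 122 = 118 |
| Both tablets together at bedtime | 2 | 1200 mg | 100% of the total, once a day | 0 |
| Two separate doses, with the advice covering only the later one | 2 | 1200 mg | 100% | 0 |

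The synopsis and Section 8.4.3 weigh against the first two readings because both say twice daily. Neither mentions the bedtime sentence or a time of day, so neither says how it is to be applied.

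**Step 3. Ask whether a misreading would be seen.** Under the first reading about half the carton comes back (118/240 = 49%), which the month-4 pill count would show. The contact at 3-4 weeks covers compliance and could show it sooner. The diary asks for the day of intake, not the number or time of doses, so one and two tablets a day can look alike in it. Neither the diary nor the pill count separates the second reading from the third.

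**Step 4. Tablet strength.** Read alone, the Section 8.3.1 sentence could mean 600 mg in each tablet or 600 mg across two tablets (300 mg each). With 300 mg tablets, 1200 mg a day needs 1200 / 300 = 4 tablets, and a carton lasts 240 / 4 = 60 days. That contradicts the four-month supply. Only 600 mg per tablet agrees with the synopsis, Section 8.3.3 and Section 8.4.2 together.

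**Step 5. Carton against visit interval.** At two a day a carton lasts 240 / 2 = 120 days. Counting four calendar months from every start date in 2016-2019 gives 120 days for 19% of dates, 121 for 13%, 122 for 44% and 123 for 24%, with a mean of 121.7. The gap is therefore 0 to 3 days (0 to 6 tablets) per interval, on average 1.7 / 121.7 = 1.4%. With full adherence until the carton is empty, the share of calendar-day doses taken is 240 / (2 × days): 100%, 99.2%, 98.4% and 97.6% for 120, 121, 122 and 123 days.

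A late visit widens the gap. The documents state no window, so as an assumption take a visit 7 or 14 days after day 120: 240 / (2 × 127) = 94.5% and 240 / (2 × 134) = 89.6%.

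**The case against.** The strongest reply is that the regimen is clear from the whole document. The bedtime sentence only encourages, it follows a plain twice-daily statement, and the section headed as administration instructions says twice daily without qualification. A participant on one tablet a night would have to pass the early contact and then return half a carton unnoticed. This stands as far as it limits duration: halved intake throughout the trial is a worst case, and the documents give no basis for estimating how many participants would be affected. They also give no human dose-response for stone events, so no loss of power can be computed. The reply does not remove the defect, because the sentence remains unreconciled and the diary would not expose the error.

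A reader might infer more than the documents support:

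- **That Section 8.1 contradicts the regimen.** It does not. 1200 mg is the daily total of 600 mg taken twice.
- **That pill-count compliance has no denominator.** Two tablets a day follows from Section 8.4.3 with Sections 8.3.3 and 8.4.2.
- **That the supply shortfall builds up to 16 days.** Nine cartons hold 9 × 240 = 2,160 tablets against 2,190 to 2,192 for 36 months, a difference of 30 to 32. That figure sums nine separate gaps. Each dispensing starts afresh, no on-time gap exceeds 3 days, and with 30-day months there is none.
- **That any single missed dose is a protocol violation.** Section 13 lists failure to take the prescribed dosage daily, within a definition limited to significant requirements. It does not say that one missed dose qualifies.

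**Conclusion.** The point holds as an internal inconsistency in Section 8.4.1. Twice-daily dosing and a single tablet at bedtime stand in the same paragraph, and no other section says how they combine. The largest consequence is 50% of planned intake for a participant who reads the advice as one tablet a night. This rests on 600 mg per tablet, and it lasts only until the misreading is noticed. How often it would occur, and what it would do to the treatment effect, cannot be estimated from the documents.

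The other two items are minor. Section 8.3.1 is loosely worded, not unresolvable. The carton is 0 to 3 days short per on-time interval, about 1.4% on average. It deserves a note because no overage or visit window is stated and resupply is described only at visits. Neither item would justify a finding alone.

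**What to change.** The sponsor should reconcile the bedtime sentence in Section 8.4.1 with the twice-daily statements in that section, Section 8.4.3 and the synopsis, so that one regimen and one time-of-day instruction appear in the protocol, the carton directions and the diary. Which text governs is for the sponsor to decide; no dose or schedule is proposed here.

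In the same edit:

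- Reword Section 8.3.1 so that the strength of each tablet is explicit and agrees with the synopsis and Sections 8.3.3 and 8.4.2.
- Align carton size with visit spacing, for example by stating the interval in days or by matching the quantity dispensed to it.

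The cost is a wording amendment to the protocol, label and diary, and possibly a few more tablets per carton (at most 2 × 123 − 240 = 6 for an on-time visit). The sample size and the analysis are unaffected.

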### 8.4.2 Dispensing

The ALA supplement or placebo will be given to the participant with sufficient quantity for administration at home, with a 4-month supply (240 tablets) to be given at each interval visit. At subsequent visits, remaining pills will be counted and counts recorded to reflect compliance for participants.

### 8.4.3 Administration Instructions

The ALA supplement or placebo is to be taken orally twice daily.

### 8.4.4 Storage

The ALA supplement will be stored under dry conditions and at room temperature in a locked cabinet in a locked office within the Compounding and Research Support Pharmacy at UCSF.

## **8.5 Study Drug Accountability**

An accurate and current accounting of the dispensing and return of study drug for each participant will be maintained on an ongoing basis by a member of the study team. The number of study drug dispensed and returned by the participant will be recorded on the Investigational Drug Accountability Record. A member of the study team will verify these documents throughout the course of the study. After participants are enrolled at 3-4 weeks, a study coordinator will contact each participant to check compliance, tolerability, and side effects with ALA supplementation.

## **8.6 Measures of Treatment Compliance**

Participants will be asked to keep a diary noting the day and date they take their study drug and any adverse events. They will be asked to bring their participant diary to each study visit along with all used and unused study drug containers.

# **9 STUDY PROCEDURES AND GUIDELINES**

A Schedule of Events representing the required testing procedures to be performed for the duration of the study is diagrammed in Appendix 1.

Prior to conducting any study-related activities, written informed consent and the Health Insurance Portability and Accountability Act (HIPAA) authorization must be signed and dated by the participant or participant's legal representative. If appropriate, assent must also be obtained prior to conducting any study-related activities.

## **9.1 Clinical Assessments**

### **9.1.1 Concomitant Medications**

All concomitant medication and concurrent therapies will be documented at baseline/screening initial visit and at all Study Visits (as is the current standard for clinical care), and at early termination when applicable. Dose, route, unit frequency of administration, and indication for administration and dates of medication will be captured.

### **9.1.2 Demographics**

Demographic information (date of birth, gender, race) will be recorded at the initial visit.

### **9.1.3 Medical History**

Relevant medical history, including history of current disease, other pertinent family and social history, and information regarding underlying diseases will be recorded at the initial visit. The determination of symptomatic stone recurrences, defined as renal colic, stone passage, or surgical removal of a stone will be performed.

### **9.1.4 Physical Examination**

A complete physical examination will be performed by either the investigator or a sub investigator who is a physician at the initial visit. Qualified staff (MD, NP, RN, and PA) may complete the abbreviated physical exam at all other visits. New abnormal physical

exam findings must be documented and will be followed by a physician or other qualified staff at the next scheduled visit.

### **9.1.5 Vital Signs**

Body temperature, blood pressure, pulse and respirations will be performed every 4 months as part of their routine normally scheduled visits.

### **9.1.6 Other Clinical Procedures**

Imaging studies will be performed at scheduled clinic visits as medically needed and at the discretion of the investigator. The imaging studies may include plain KUB x-ray and renal ultrasound, or CT scan if medically necessary (see below). This information will allow determination of silent stone recurrences classified as stone growth or new stones compared to prior radiologic exams. All participants will undergo low dose non-contrast CT scans at the end of the three years of study drug treatment (Visit10). This non-contrast CT scan at the end of the three-year study period will be considered a research imaging study (not a part of routine clinical care) and paid for by study funding.

In addition, quality of life surveys with Wisconsin Stone-QoL will be administered during regularly scheduled clinic visits.

If participants collect stones that pass during the course of the study, these will also be collected and analyzed for composition.

All of these clinical procedures are part of the current standard of care for patients with cystinuria undergoing management at UCSF with the exception of the CT scan performed at the completion of the study. With the exception of this radiographic study, the current study will not alter standard clinical care for participants.

### **9.1.7 Adverse Events**

Information regarding occurrence of adverse events will be captured throughout the study. Duration (start and stop dates and times), severity/grade, outcome, treatment and relation to study drug will be recorded on the case report form (CRF).

## **9.2 Clinical Laboratory Measurements**

### **9.2.1 Blood Chemistry Profile**

Blood tests will include CBC, chemistries, BUN, and creatinine that will be collected at regularly scheduled clinic visits as medically needed and at the discretion of the investigator. During routine visits for blood tests, any discarded blood will be collected for research testing. No additional blood will be taken outside of their normal routine medical care.

### **9.2.2 Pregnancy Test**

No participant who is pregnant or is planning to be pregnant will be allowed into the study

per the exclusion criteria.

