## 6.2 Inclusion Criteria

Inclusion criteria will include: males and females age 18 or older; documented cystinuria on prior 24-hour urine collection and/or stone analysis; history of previous cystine kidney stones; and being able and willing to provide consent.

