## 6.3 Exclusion Criteria

Exclusion criteria will include: poorly controlled diabetes mellitus (hemoglobin A1C > 8.0% for more than 1 year); current ALA administration at the time of screening; ALA administration within the last year prior to screening; vulnerable populations including incarceration status; anticipation of pregnancy during the study duration; unable to give informed consent; non-English primary language; pregnancy, lactation, or child-bearing age without birth control devices; and serious illness likely to cause death within the next 5 years.

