### 9.2.3 Urinalysis

Routine urinalysis (glucose, protein, blood, nitrite, pH) and 24-hour urine collections for quantitative urinary cystine (Litholink, Chicago, IL) will be performed at regularly scheduled clinic visits as medically needed and at the discretion of the investigator. Urinary metabolomic and metallomic profiles will be performed on urine collected at regularly scheduled clinic visits. No additional urinalysis studies will be collected outside of their normal routine medical care.

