## 12 DISCONTINUATION AND REPLACEMENT OF PARTICIPANTS

### 12.1 Early Discontinuation of Study Drug

A participant may be discontinued from study treatment at any time if the participant, the investigator, or the Sponsor/Investigator feels that it is not in the participant's best interest to continue. The following is a list of possible reasons for study treatment discontinuation:

- Participant withdrawal of consent (or assent)
- Participant is not compliant with study procedures
- Adverse event that in the opinion of the investigator would be in the best interest of the participant to discontinue study treatment
- Protocol violation requiring discontinuation of study treatment
- Lost to follow-up
- Sponsor request for early termination of study
- Positive pregnancy test (females)

If a participant is withdrawn from treatment due to an adverse event, the participant will be followed and treated by the Investigator until the abnormal parameter or symptom has resolved or stabilized.

All participants who discontinue study treatment should come in for an early discontinuation visit as soon as possible and then should be encouraged to complete all remaining scheduled visits and procedures.

All participants are free to withdraw from participation at any time, for any reason, specified or unspecified, and without prejudice.

Reasonable attempts will be made by the investigator to provide a reason for participant withdrawals. The reason for the participant's withdrawal from the study will be specified in the participant's source documents (Refer to Section 10) for early termination procedures.

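### No pregnancy test is scheduled to support the pregnancy exclusion, the positive-test reason for stopping treatment, or the month-36 research CT

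*Combined protocol and SAP*

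**What the plan says.** Section 6.2 admits "males and females age 18 or older". Section 6.3, repeated in the synopsis, excludes "anticipation of pregnancy during the study duration" and also "pregnancy, lactation, or child-bearing age without birth control devices". Section 9.2.2 is headed Pregnancy Test, but its whole content is a restatement of that exclusion: "No participant who is pregnant or is planning to be pregnant will be allowed into the study". Section 12.1 gives, among possible reasons for stopping study treatment, "Positive pregnancy test (females".

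Section 9 identifies where required testing is to be found: "A Schedule of Events representing the required testing procedures to be performed for the duration of the study is diagrammed in Appendix 1". Three places limit what may be collected. Section 4.1 rules out any extra blood draw or urine collection for the study, Section 9.2.1 rules out blood beyond routine care, and Section 9.2.3 states that "No additional urinalysis studies will be collected outside of their normal routine medical care".

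On the end-of-treatment scan, Section 9.1.6 says "All participants will undergo low dose non-contrast CT scans at the end of the three years of study drug treatment". The same section classes that scan as research imaging outside routine care, paid for by the study.

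**The concern.** The protocol relies on pregnancy status in three places: at entry, while the participant is on study product, and implicitly when it sends every participant for an abdominal CT done only for research. The wording of Section 12.1 presupposes that a test result will exist, and Section 9.2.2 has the heading under which a test would be described. Yet a coordinator working from the visit lists and Appendix 1 meets no instruction to test, and meets three statements that point against taking a sample for one.

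What is at stake is participant safety. Section 8.2 places randomisation at the first screening visit, product is then taken for three years, and visits are four months apart. A pregnancy too early to be recognised at Visit 1, or one that begins shortly before the month-36 scan, is the case that history and self-report are least able to detect. The plan treats pregnancy outcomes as relevant, since Section 11.2 counts a congenital anomaly as a serious adverse experience.

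**Working it through.** No formula applies and the plan states no figure to reproduce. The check is to read each place where a pregnancy test could be specified and compare it with the rules that depend on one.

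| Place | What it contains | Pregnancy test |
|---|---|---|
| 9.2.2 Pregnancy Test | Restates the exclusion; no type, timing or frequency | None |
| 9.2.1 Blood Chemistry Profile | Blood count, chemistries, BUN, creatinine | None |
| 9.2.3 Urinalysis | pH, nitrite, blood, protein, glucose; 24-hour cystine | None |
| 10.1 Visit 1 | 11 items, from consent to specimen collection | None |
| 10.2 Visits 2-9 | 11 items | None |
| 10.3 Visit 10 | 10 items; research CT is item 8 | None, and none before item 8 |
| 10.4 Visits 11-16 | 10 items | None |
| 10.5 Early withdrawal | 11 items | None |
| Appendix 1 | 15 rows | None |

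Scheduled visits: 1 (Visit 1) + 8 (Visits 2-9) + 1 (Visit 10) + 6 (Visits 11-16) = 16. Pregnancy tests scheduled across them: 0.

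Next, each dependent rule is set against what the schedule supplies.

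1. **Exclusion at entry (6.3).** Visit 1 supplies a medical history, a concomitant medication record and a complete physical examination. These can establish intention to conceive, use of birth control and a known pregnancy. They cannot reliably establish the absence of an early one. No step confirming status is listed before randomisation or dispensing.
2. **Positive test as a reason to stop (12.1).** The only positive results that could reach the investigator are from tests ordered in ordinary care or reported by the participant, because the study orders none.
3. **Month-36 CT (9.1.6, 10.3).** It applies to all participants and is not routine care. No pregnancy check precedes it in the visit list, and Section 9.1.6 states no exception.

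Finally, could a site add a test on its own initiative? Sections 4.1, 9.2.1 and 9.2.3 read against a new sample. An existing sample is not assured either. Section 10.1 and Appendix 1 list 24-hour urine at Visit 1, but Section 9.2.3 makes urine testing depend on medical need and investigator discretion, and the opening of Section 10 makes Visit 1 urine conditional on medical necessity.

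**The case against.** A reader might infer that neither rule can work at all, or that pregnancy status is never checked. The documents do not support that. History is taken at Visit 1. Appendix 1 marks medical history, medications and a physical examination at every visit, and adverse experiences from Visit 2. A coordinator contacts participants at 3-4 weeks. The birth-control and anticipated-pregnancy criteria can be applied by interview. Section 12.1 does not require the positive test to be a study test, and it lists possible reasons, so stopping is permitted and not mandated. The sections can all be followed as written, so this is a missing procedure and not a flat contradiction between rules. All of this stands. What remains is that every one of these routes depends on the pregnancy already being known or suspected.

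A reader might also want an expected number of pregnancies. The documents give neither the number of participants who could become pregnant nor a contraceptive failure rate. A count of all on-treatment pregnancies would also be the wrong measure, because the specific gap is an unrecognised pregnancy at entry or at the scan.

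A third objection is that the consent form, the package insert in Appendix 2, the study manual cited in Section 11.1, or the imaging unit's own practice may provide for testing. None of these can be seen here, and any of them might reduce the practical risk. None would put a test into the schedule that Section 9 makes the list of required procedures.

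**Conclusion.** The point holds as a gap in the schedule. The protocol excludes pregnancy and names a positive pregnancy test as a possible reason to stop treatment, but it schedules no test at any of 16 visits and none before a research CT that all participants undergo. Both rules rest on history, self-report or outside testing, which can miss an early unrecognised pregnancy at randomisation or before the scan.

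The conclusion rests on the visit lists, laboratory sections and Appendix 1, which are legible and agree on this point. It needs no assumption about pregnancy rates, and no number of affected participants is claimed. The gap does not touch the primary endpoint or its analysis. It warrants correction because a safety exclusion and a study-only scan depend on a status that the schedule never measures, and because the correction is small.

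**What to change.** Reconcile Sections 4.1, 6.3, 9.1.6, 9.2.1 to 9.2.3, 10.1 to 10.5, 12.1 and Appendix 1 (with the matching synopsis text) so that the exclusion, the discontinuation reason and the research CT rest on a pregnancy check that Appendix 1 actually contains. Give Section 9.2.2 the procedural content its heading promises. Amend the sentences in Sections 4.1, 9.2.1 and 9.2.3 that bar additional blood or urine so that they permit the check. Changing 9.2.3 alone would leave 4.1 in conflict. The type, timing and frequency of the check are for the sponsor to set.

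The cost is protocol and consent wording and a simple test for a subset of 50 participants at visits that already exist. The sample may sometimes be one that would not otherwise have been collected, so the amendment should not assume that urine is always at hand.
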